### **5.2.2** Pre-Registration Requirements FOR NON-CANADIAN INTERNATIONAL INSTITUTIONS

#### **5.2.2.1** For institutions that do not have an approved LOI for this protocol:

International sites must receive written approval of submitted LOI forms from RTOG Headquarters prior to submitting documents to their local ethics committee for approval. See [http://www.rtog.org/pdf\\_forms.html?members/forms=Intl\\_LOI\\_Form.doc](http://www.rtog.org/pdf_forms.html?members/forms=Intl_LOI_Form.doc)

#### **5.2.2.2** For institutions that have an approved LOI for this protocol:

All requirements indicated in your LOI Approval Notification must be fulfilled prior to enrolling patients to this study.

## **5.3** Pre-registration Requirements for SBRT

Participating Institutions must be credentialed for stereotactic body radiation therapy and heterogeneity corrections by the Advanced Technology Consortium (ATC) prior to enrolling patients on this study. Institutions wishing to submit IMRT plans must also be credentialed for intensity modulated radiotherapy (IMRT) by the Advanced Technology Consortium (ATC) prior to enrolling patients on this study. Sites using CyberKnife™ equipment must be credentialed for dose painting IMRT prior to enrolling patients on study.

As it pertains to this study, the ATC includes the Image-Guided Therapy Center (ITC) at Washington University, St. Louis; the Radiological Physics Center (RPC) at MD Anderson Cancer Center; and RTOG RT Quality Assurance.

Credentialing includes the following 5 steps (Sections 5.3.1-5.3.5): Centers previously credentialed for some of the technologies/procedures involved may be absolved from re-credentialing. However, institutions previously credentialed to use Clarkson or pencil beam algorithms for SBRT on RTOG 0236 by the ATC will be required to be re-credentialled for heterogeneity corrections. In addition, institutions that change the technology/procedures

previously credentialed (i.e., fundamentally change methods like changing from tracking to abdominal compression for motion control) must be re-credentialed with their new systems.

- 5.3.1** (2/16/10) Each participating institution must complete the 3D QA Facility Questionnaire for SBRT available on the ATC web site, <http://itc.wustl.edu>. Each institution must submit the completed Facility Questionnaire by e-mail, fax, or mail to:

- 5.3.4** Each participating institution must irradiate a standardized phantom provided by the Radiological Physics Center (RPC) at MD Anderson Cancer Center. Instructions for requesting and irradiating the phantom are available at the RPC web site, <http://rpc.mdanderson.org/rpc/> by selecting "Credentialing" and "RTOG." The phantom simulates a lung tumor within lung tissue equivalent material. The irradiation must be within tolerances specified in Section 6.0. The treatment plan for irradiation of the phantom must be submitted electronically to the ITC (see Section 5.1.2).

- 5.3.5** Each participating institution must successfully complete and submit a protocol-specific Dry-Run Test, the treatment plan for the first patient to be treated at the site on this protocol PRIOR TO DELIVERING ANY PROTOCOL TREATMENT. The plan will be reviewed centrally at the ITC, and suggestions regarding protocol compliance will be forwarded to the participating institution. The treatment plan for subsequent patients enrolled at a site will not be required to be centrally reviewed prior to treatment, but will be reviewed for protocol compliance at a later date.

#### **5.4 Dial-in Registration Only**

**Note: Patients cannot be web registered for this study.**

Patients can be registered only after eligibility criteria are met. The Eligibility Checklist must be completed in its entirety prior to calling RTOG. The completed, signed, and dated Checklist used at study entry must be retained in the patient's study file and will be evaluated during an institutional NCI/RTOG audit.

Patients can be registered prior to any protocol therapy by calling RTOG Headquarters at [contact], Monday through Friday, 8:30 a.m. to 5:00 p.m. EST. Patients will be assigned to an SBRT dose level based on the data available through the previous day. For further details, see Section 13.3.

### **6.0 RADIATION THERAPY**

**Note: Intensity Modulated RT (IMRT) is allowed, but sites that wish to use IMRT must be credentialed for heterogeneity corrections and IMRT for RTOG lung studies (see Section 5.3).**

**Protocol treatment must begin within 1-3 weeks after registration.**

#### **6.1 Dose Specifications**

##### **6.1.1 Stereotactic Targeting and Treatment**

SBRT has now been formally defined and described in a published guideline from the American College of Radiology and American Society for Therapeutic Radiology and Oncology. This protocol will respect that guideline. The term stereotactic for the purposes of this protocol implies the targeting, planning, and directing of therapy using beams of radiation along any trajectory in 3-D space toward a target of known 3-D coordinates. The coordinate system is defined by reliable "fiducial" markers. This differs from conventional radiation therapy, in which therapy is directed toward less-than-reliable skin marks or bony landmarks that are indirectly referenced to the tumor (surrogates). This protocol will require treatments to be conducted with the use of a fixed 3-D coordinate system defined by fiducials. The coordinate system defined by the fiducials should be directly related to the radiation-producing device (e.g., couch and gantry) in a reproducible and secure fashion. Capability should exist to define the position of targets within the patient according to this same 3-D coordinate system. As such, the patient is set up for each treatment with the intention of directing the radiation toward an isocenter or target according to the known 3-D coordinates as determined in the process of treatment planning. The nature of the fiducials themselves may include radiopaque markers or rods placed at known locations in a frame or fixed structure adjacent to the patient as well as use of the tumor itself as a fiducial (e.g., acquiring tomographic views of the tumor simultaneously with the treatment). Metallic "seeds" placed within the tumor will be allowed to constitute a fiducial so long as the methods are validated and a plan is in place to identify seed migration (e.g., redundant seeds placed).

##### **6.1.2 Dose Fractionation**

Patients will receive 5 fractions of radiation, on an every 2-day basis i.e., 2-3 treatments per week, so that the SBRT schedule is completed within 1.5-2 weeks. There should be a minimum of 40 hours between treatments.

**The starting dose level will be dose level 5: 10 Gy x 5 fractions, i.e., 50 Gy /5 fractions.** The dose per fraction for each patient will be provided at the time of registration based on the toxicity experience of the previous patients on study.

The dose per fraction is to be prescribed to the prescription line at the edge of the PTV.

Dose Level	Dose per Fraction	Total Dose
1	8 Gy	40 Gy
2	8.5 Gy	42.5 Gy
3	9 Gy	45 Gy
4	9.5 Gy	47.5 Gy
5	10 Gy†	50 Gy
6	10.5 Gy	52.5 Gy

7	11 Gy	55 Gy
8	11.5 Gy	57.5 Gy
9	12 Gy	60 Gy

†Protocol treatment begins at Level 5, 10 Gy. Levels 1-4 will be employed if dose-limiting toxicity is seen with the Level 5 (10 Gy) dose.

### 6.1.3 Premedications

Corticosteroid premedication will not be mandated, although it can be used at the discretion of the treating oncologist (in which case, its use needs to be reported). Analgesic premedication to avoid general discomfort during long treatment durations is recommended when appropriate.

## 6.2 Technical Factors

### 6.2.1 Physical Factors

Only photon (x-ray) beams with photon energies 4-10 MV will be allowed. Cobalt-60 and charged particle beams (including electrons, protons, and heavier ions) are not allowed. Photon beam energies > 10 MV but not > 15 MV will be allowed only for a limited number ( $\leq 2$ ) beams that must travel more than a cumulative distance of 10 cm through soft tissue (not lung) to reach the isocenter.

### 6.2.2 Minimum Field Aperture (Field Size) Dimension

Because of uncertainties in beam commissioning resulting from electronic disequilibrium within small beam apertures, a minimum field dimension of 3.5 cm is required for any field used for treatment delivery. It is understood that this may exceed the technical requirements listed in Section 6.4 for small lesions (< 2.5 cm axial GTV dimension or < 1.5 cm craniocaudal GTV dimension). In such cases, the prescription dose is still prescribed to the edge of the defined PTV. This minimum field dimension does not apply to centers using tomotherapy or multiple pencil beam delivery systems.

### 6.2.3 Dose Verification at Treatment

Personal dosimeter measurements (e.g., diode, TLD) may be obtained for surface dose verification for accessible beams as per institutional preference. This information is not required by the protocol.

## 6.3 Localization, Simulation, and Immobilization

### 6.3.1 Patient Positioning

Patients will be positioned in a stable position capable of allowing accurate reproducibility of the target position from treatment to treatment. Positions uncomfortable for the patient should be avoided so as to prevent uncontrolled movement during treatments. A variety of immobilization systems may be used, including stereotactic frames that surround the patient on three sides and large rigid pillows (conforming to patients' external contours) with reference to the stereotactic coordinate system (see Section 6.1). Patient immobilization must be reliable enough to ensure that the gross tumor volume (GTV) does not deviate beyond the confines of the planning treatment volume (PTV) as defined in Section 6.4 with any significant probability (i.e., < 5%).

### 6.3.2 Inhibition of Effects of Internal Organ Motion

Special considerations must be made to account for the effect of internal organ motion (e.g., breathing) on target positioning and reproducibility. Acceptable maneuvers include reliable abdominal compression, accelerator beam gating with the respiratory cycle, tumor tracking, and active breath-holding techniques. All systems used to account for internal organ motion must be validated and accredited by the Principal Investigator and Study Co-Chairs before enrolling or treating patients on this trial. Internal organ inhibition maneuvers must be reliable enough to insure that the GTV does not deviate beyond the confines of the PTV as defined in Section 6.4 with any significant probability (i.e., < 5%).

### 6.3.3 Localization

Isocenter or reference point port localization images (anterior/posterior and lateral) should be obtained at each treatment on the treatment unit (or patients should undergo a tomographic imaging study using the linear accelerator couch, if available) immediately before treatment to ensure proper alignment of the geometric center (i.e., isocenter) of the simulated fields. Verification CT scans and portal films may be taken at the discretion of the participating institution but are not required for protocol participation. The localization verification images will be submitted for quality assurance (QA) purposes to the ITC. Centers with tomographic imaging study capability using the linear accelerator couch should create digitally reconstructed radiograph (DRR) images of the anterior/posterior and lateral alignment to be submitted for QA purposes to the ITC.

## **6.4 Treatment Planning/Target Volumes**

### **6.4.1 Image Acquisition**

Computed tomography will be the primary image platform for targeting and treatment planning. The planning CT scans must allow simultaneous view of the patient anatomy and fiducial system for stereotactic targeting and must be done with *IV* contrast unless the patient has allergic problems with contrast or has renal insufficiency. Contrast will allow better distinction between tumor and adjacent vessels or atelectasis. Axial acquisitions with gantry 0 degrees will be required with spacing  $\leq 3.0$  mm between scans in the region of the tumor. Images will be transferred to the treatment planning computers via direct lines, disc, or tape.

Helical and four-dimensional CT (4DCT) is permitted for the study. Using either approach, the target lesion will be outlined by an appropriately trained physician and designated the gross tumor volume. The target will generally be drawn using CT pulmonary windows; however, soft tissue windows with contrast may be used to avoid inclusion of adjacent vessels, atelectasis, or mediastinal or chest wall structures within the GTV. This target will not be enlarged whatsoever for prophylactic treatment (including no "margin" for presumed microscopic extension); rather, include only abnormal CT signal consistent with gross tumor (i.e., the GTV and the clinical target volume [CTV] are identical).

An additional 0.5 cm in the axial plane and 1.0 cm in the longitudinal plane (craniocaudal) will be added to the GTV to constitute the PTV for centers acquiring image datasets using helical scanning. The methodology employed for centers incorporating 4DCT image datasets into target definition and treatment planning must first be approved through the process described in Section 5.3.2. Institutions using 4DCT must provide on a per-person basis the following information: method of image acquisition, utilization of the 4DCT image datasets, and the expansion margin to define the PTV. In addition, for each plan the target motion measured from 4DCT must be submitted.

There are many valid approaches to defining target volumes and margins using multiple datasets representing different phases of the breathing cycle. These include but not limited to:

- a. the ITV (Internal Target Volume) concept from ICRU 62 with an appropriate margin accounting for geometric uncertainties (uniform 5 mm recommended) to define the PTV;
- b. the mean target position with an appropriate margin to account for target motion and geometric uncertainties to define the PTV;
- c. two helical scans, one scan with the patient at inhale breath-hold and the second scan with patient at exhale breath-hold.

The following will be required in terms of documenting target motion:

1. For particular method of target motion suppression (abdominal compression, breath hold, etc.), keep a tally of target motion range for each patient treated. Describe clearly the method utilized in the measurement of range of target motion and provide estimated error of measurement. Justify the estimation of error.
2. It is preferable to have information on range of motion along each axis of pt body (sup-inf, ap-pa, lt-rt). In case such information is not available, provide range of motion in 1 or 2 directions with clear indication of the orientation of the axis along which the motion range is evaluated.
3. In case of multiple measurements of ranges of motion (at simulations and/or at treatments, possibly pre- and post-treatments) provide information about the day and time when the data have been collected.
4. When data for some patients/treatment fractions is not collected the record of the missing measurement has to be kept and reported. If there is a clinical reason for not collecting data, it needs to be reported as well.
5. The reported range of motion has to be separated from setup errors.

### **6.4.2 Dosimetry**

#### **6.4.2.1 3D Conformal Planning**

Three-dimensional coplanar or non-coplanar beam arrangements will be custom designed for each case to deliver highly conformal prescription dose distributions. Non-opposing, non-coplanar beams are preferable. Typically,  $\geq 10$  beams of radiation will be used with roughly equal weighting. Generally, more beams are used for larger lesion sizes. When static beams are used, a minimum of seven non-opposing beams should be used. For arc

rotation techniques, a minimum of 340 degrees (cumulative for all beams) should be utilized. For this protocol, the isocenter is defined as the common point of gantry and couch rotation for the treatment unit. Field aperture size and shape should correspond nearly identically to the projection of the PTV along a beam's eye view (i.e., no additional "margin" for dose buildup at the edges of the blocks or MLC jaws beyond the PTV). The only exception will be when observing the minimum field dimension of 3.5 cm when treating small lesions (see above). As such, prescription lines covering the PTV will typically be the 60-90% line (rather than 95-100%); however, higher isodoses (hotspots) must be manipulated to occur within the target and not in adjacent normal tissue. The isocenter in stereotactic coordinates will be determined from system fiducials (or directly from the tumor in the case of volumetric imaging) and translated to the treatment record.

The treatment dose plan will be made up of multiple static beams or arcs as described above. The plan should be normalized to a defined point corresponding closely to the center of mass of the PTV (COMPTV). Typically, this point will be the isocenter of the beam rotation; however, it is not a protocol requirement for this point to be the isocenter. Regardless, the point identified as COMPTV must have defined stereotactic coordinates and receive 100% of the normalized dose. Because the beam apertures coincide nearly directly with the edge of the PTV (little or no added margin), the external border of the PTV will be covered by a lower isodose surface than usually used in conventional radiotherapy planning, typically around 80% but ranging from 60-90%. The prescription dose will be delivered to the margin of the PTV and fulfill the requirements below. As such, a "hotspot" will exist within the PTV centrally at the COMPTV with a magnitude of prescribed dose times the reciprocal of the chosen prescription isodose line (i.e., 60-90%).

#### **6.4.2.2** Intensity Modulated Radiation Therapy (IMRT)

IMRT is allowed in this study, provided that the participating institution is credentialed by the RTOG for intra-thoracic IMRT treatments. The NCI Guidelines for the Use of IMRT can be found on the RTOG homepage, <http://www.rtog.org/>.

The use of IMRT in this study is at the discretion of the participating institution. However, IMRT should be considered only when target coverage, OAR dose limits, or dose spillage are not achievable with 3D conformal planning. In addition, IMRT plans should follow the same planning principles as discussed above for 3D conformal planning. The number of segments (control points) and the area of each segment should be optimized to ensure deliverability and avoid complex beam fluences. Ideally, the number of segments should be minimized (2-3 segments per beam should be adequate), and the area of each segment should be maximized (the aperture of one segment from each beam should correspond to the projection of the PTV along a beam's eye view).

#### **6.4.2.3** Dose Calculations

For purposes of dose planning and calculation of monitor units for actual treatment, this protocol will require tissue density heterogeneity correction (RTOG 0236 did not allow heterogeneity correction). The particular algorithm used for such correction must be approved by the RTOG Physics Committee in advance.

For purposes of this protocol, superposition/convolution dose calculation algorithms demonstrate agreement between planned versus delivered dose. Institutions with treatment planning software utilizing superposition/convolution dose calculation algorithms will need to complete a questionnaire and submit a digital "dry-run" test to the ITC. Institutions using alternative algorithms (i.e., Clarkson or pencil beam) will need to credential their treatment planning system by irradiating the Radiation Physics Center (RPC) lung phantom. Doses falling within criteria established by the Medical Physics Committee will be deemed acceptable. The criteria for acceptable agreement between measured doses in the RPC lung phantom and calculated doses using older algorithms are: Across the PTV, the agreement shall be within 5% or 5 mm.

Successful treatment planning will require accomplishment of all of the following criteria:

1. Normalization: The treatment plan should be normalized such that 100% corresponds to the center of mass of the PTV (COMPTV). This point will typically also correspond (but is not required to correspond) to the isocenter of the treatment beams.

2. **Prescription Isodose Surface Coverage:** The prescription isodose surface will be chosen such that 95% of the target volume (PTV) is conformally covered by the prescription isodose surface and 99% of the target volume (PTV) receives a minimum of 90% of the prescription dose.
3. **Target Dose Heterogeneity:** The prescription isodose surface selected in number 2 (above) must be  $\geq 60\%$  of the dose at the center of mass of the PTV (COMPTV) and  $\leq 90\%$  of the dose at the center of mass of the PTV (COMPTV). The COMPTV corresponds to the normalization point (100%) of the plan as noted in number 1 above.
4. **High Dose Spillage:**
  - a. **Location:** Any dose  $> 105\%$  of the prescription dose should occur primarily within the PTV itself and not within the normal tissues outside the PTV. Therefore, the cumulative volume of all tissue outside the PTV receiving a dose  $> 105\%$  of prescription dose should be no more than 15% of the PTV volume.
  - b. **Volume:** Conformality of PTV coverage will be judged such that the ratio of the volume of the prescription isodose meeting criteria 1 through 4 to the volume of the PTV is ideally  $< 1.2$  (see table below). These criteria will not be required to be met in treating very small tumors ( $< 2.5$  cm axial GTV dimension or  $< 1.5$  cm craniocaudal GTV dimension) in which the required minimum field size of 3.5 cm (see Section 6.2) results in the inability to meet a conformality ratio of 1.2.
5. **Low Dose Spillage:** The falloff gradient beyond the PTV extending into normal tissue structures must be rapid in all directions and meet the following criteria:
  - a. **Location:** The maximum total dose over all fractions in Gray (Gy) to any point 2 cm or greater away from the PTV in any direction must be no greater than  $D_{2cm}$  where  $D_{2cm}$  is given by the table below.
  - b. **Volume:** The ratio of the volume of 50% of the prescription dose isodose to the volume of the PTV must be no greater than  $R_{50\%}$  where  $R_{50\%}$  is given. See Table 1 below.
6. Respect all critical organ dose-volume limits listed in Section 6.5.1 below.

**Table 1: Conformality of Prescribed Dose for Calculations Based on Deposition of Photon Beam Energy in Heterogeneous Tissue**

PTV Volume (cc)	Ratio of Prescription Isodose Volume to the PTV Volume		Ratio of 50% Prescription Isodose Volume to the PTV Volume, $R_{50\%}$		Maximum Dose (in % of dose prescribed) @ 2 cm from PTV in Any Direction, $D_{2cm}$ (Gy)		Percent of Lung Receiving 20 Gy Total or More, $V_{20}$ (%)	
	Deviation		Deviation		Deviation		Deviation	
	None	Minor	None	Minor	None	Minor	None	Minor
1.8	<1.2	<1.5	<5.9	<7.5	<50.0	<57.0	<10	<15
3.8	<1.2	<1.5	<5.5	<6.5	<50.0	<57.0	<10	<15
7.4	<1.2	<1.5	<5.1	<6.0	<50.0	<58.0	<10	<15
13.2	<1.2	<1.5	<4.7	<5.8	<50.0	<58.0	<10	<15
22.0	<1.2	<1.5	<4.5	<5.5	<54.0	<63.0	<10	<15
34.0	<1.2	<1.5	<4.3	<5.3	<58.0	<68.0	<10	<15
50.0	<1.2	<1.5	<4.0	<5.0	<62.0	<77.0	<10	<15
70.0	<1.2	<1.5	<3.5	<4.8	<66.0	<86.0	<10	<15
95.0	<1.2	<1.5	<3.3	<4.4	<70.0	<89.0	<10	<15
126.0	<1.2	<1.5	<3.1	<4.0	<73.0	>91.0	<10	<15
163.0	<1.2	<1.5	<2.9	<3.7	<77.0	>94.0	<10	<15

Note 1: For values of PTV dimension or volume not specified, linear interpolation between table entries is required.

Note 2: Protocol deviations greater than listed here as “minor” will be classified as “major” for protocol compliance (see Section 6.7).

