#### **6.7.2** Dosimetry Compliance

Section 6 describes appropriate conduct for treatment planning dosimetry. The Image-Guided Therapy Center (ITC) will evaluate plans as described in Section 6.8. Criteria for both major and minor deviations are provided in the table in Section 6.4. In addition to the criteria in Section 6.4, the table in Section 6.5 lists dose volume limits for specific organs and structures. Exceeding these limits by more than 2.5% constitutes a minor protocol violation. Exceeding these limits by more than 5% constitutes a major protocol violation.

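### Table 1 in Section 6.4.2.3 reverses the inequality on the minor-deviation D2cm limit for the two largest PTV rows (126 and 163 cc)

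*Protocol*

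**What the plan says.** Section 6.4.2.3 of the Protocol lists the criteria a treatment plan must meet. Criterion 5a concerns low-dose spillage: the maximum dose "to any point 2 cm or greater away from the PTV in any direction must be no greater than" the D2cm value in Table 1. Table 1 gives, for each of eleven PTV volumes, a limit for no deviation and a limit for a minor deviation on four measures. Up to 95 cc, all entries are upper limits. The 95 cc row reads "95.0 <1.2 <1.5 <3.3 <4.4 <70.0 <89.0 <10 <15".

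In the last two rows the sixth entry, the minor limit for D2cm, changes direction:

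- 126 cc: "126.0 <1.2 <1.5 <3.1 <4.0 <73.0 >91.0 <10 <15"
- 163 cc: "163.0 <1.2 <1.5 <2.9 <3.7 <77.0 >94.0 <10 <15"

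Two notes follow the table. Note 1 requires linear interpolation for volumes between rows. Note 2 opens "Protocol deviations greater than listed here as" minor, and classes such deviations as major. Section 6.7.2 then relies on the table for compliance scoring: "Criteria for both major and minor deviations are provided in the table in Section 6.4".

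**The concern.** A minor-deviation entry with a greater-than sign cannot work alongside criterion 5a and Note 2. Beside a no-deviation limit of `<73.0`, an entry of `>91.0` leaves the values in between without a class. It also lists as minor exactly the values that Note 2 makes major. No other section corrects the two cells.

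What is at stake is how deviations are scored for the largest targets. Under Section 5.3.5 only a site's first plan is reviewed centrally before treatment, so later patients are planned from the printed table and reviewed afterwards. Spillage beyond the PTV matters in a trial of tumors next to central organs, and the two cells that should cap the minor category for large PTVs do not cap it.

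**Working it through.** **Signs.** Table 1 has 11 rows of 8 limits, or 88 entries. Of these, 86 carry `<`. The two exceptions are the D2cm minor entries at 126 and 163 cc; the other seven entries in each of those rows carry `<`.

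**Do the figures fit?** Ignoring the signs, the D2cm columns run as follows.

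| PTV (cc) | None (%) | Minor (%) |
|---|---|---|
| 1.8 | 50 | 57 |
| 3.8 | 50 | 57 |
| 7.4 | 50 | 58 |
| 13.2 | 50 | 58 |
| 22 | 54 | 63 |
| 34 | 58 | 68 |
| 50 | 62 | 77 |
| 70 | 66 | 86 |
| 95 | 70 | 89 |
| 126 | 73 | 91 |
| 163 | 77 | 94 |

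The minor limits never fall as volume rises, and each exceeds its no-deviation limit. So 91 and 94 are plausible as upper limits, and only the sign is out of line.

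**Classification, table cells as printed and with the signs corrected.**

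| PTV (cc) | D2cm (%) | As printed | Corrected |
|---|---|---|---|
| 126 | 70 | none | none |
| 126 | 80 | no class | minor |
| 126 | 90 | no class | minor |
| 126 | 93 | minor | major |
| 126 | 100 | minor | major |
| 163 | 70 | none | none |
| 163 | 80 | no class | minor |
| 163 | 93 | no class | minor |
| 163 | 100 | minor | major |

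Width of the band without a class: 91 − 73 = 18 percentage points at 126 cc, and 94 − 77 = 17 at 163 cc.

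**Can an eligible patient reach these rows?** Section 3.1.2 allows tumors up to 5 cm. For helical CT, Section 6.4.1 says: "An additional 0.5 cm in the axial plane and 1.0 cm in the longitudinal plane (craniocaudal) will be added to the GTV". For a 4DCT internal target volume it recommends a uniform 5 mm. I assume a spherical GTV of diameter D cm.

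- Helical margins: PTV = π/6 × (D + 1)² × (D + 2). At D = 5 this is π/6 × 6 × 6 × 7 = 131.9 cc. The PTV reaches 126 cc at D = 4.90, since π/6 × 5.904² × 6.904 = 126.0. It passes 95 cc at about D = 4.35. Reaching 163 cc would need about D = 5.46, above the size limit.
- Uniform 5 mm, no added motion volume: PTV = π/6 × (D + 1)³. At D = 5 this is 113.1 cc. It passes 95 cc at about D = 4.66.

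The 126 cc row is therefore reached only near the size limit with helical margins. Because Note 1 requires interpolation, though, any PTV between 95 and 126 cc also uses the 126 cc entry, and any PTV between 126 and 163 cc uses both faulty entries.

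**Intended limits at 131.9 cc, with signs corrected.**

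- None: 73 + (131.9 − 126)/(163 − 126) × (77 − 73) = 73.6%
- Minor: 91 + (131.9 − 126)/(163 − 126) × (94 − 91) = 91.5%

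In dose, from the unrounded percentages, these are 36.8 and 45.7 Gy at a 50 Gy prescription, and 44.2 and 54.9 Gy at 60 Gy.

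**The case against.** The best answer is that the page corrects itself. The column is headed as a maximum dose, criterion 5a sets a ceiling, and Note 2 makes anything beyond the minor figure major. A value between 73% and 91% at 126 cc fails the no-deviation limit but does not exceed the listed minor figure, so by elimination it is minor; above 91%, Note 2 makes it major. Read that way, there is no unclassified band. Plans are also scored centrally by the Image-Guided Therapy Center and reviewed by the study chairs (Sections 6.7.2 and 6.8), who are unlikely to accept a minor category with no ceiling. Nothing in Section 13 uses deviation class.

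Most of this stands. The intended meaning is recoverable, and a careful scorer would probably reach it. It does not make the cells right: that reading works only by disregarding the printed sign, in a table that Section 6.7.2 makes the scoring standard.

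Two lesser points also stand. Reaching the affected rows depends on the assumed tumor shape and margin, and under the helical assumption the 163 cc row serves only as an interpolation anchor; motion volume under 4DCT could enlarge the PTV. A text-extraction fault cannot be wholly excluded without the printed page, but two isolated reversals among correctly read signs in the same rows look like a misprint in the source.

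**Conclusion.** The concern holds. Two of the eleven D2cm minor limits carry the wrong inequality and contradict criterion 5a, Note 2 and the other nine rows. Confidence in the contradiction is high; confidence that any plan was misclassified because of it is low.

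The consequence is narrow: deviation scoring on one criterion, for PTVs above 95 cc. R50%, V20 and the organ limits in Tables 2 and 3 are intact and can still produce a major deviation. Dose assignment, DLT determination, the MTD and the tumor-control analysis are untouched. The document does not allow the number of affected patients to be derived. That the 126 cc row can be reached rests on a spherical GTV and the helical margins.

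**What to change.** Change the two cells to `<91.0` and `<94.0`. The classes then become:

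- 126 cc: below 73% none; 73% to below 91% minor; 91% or more major.
- 163 cc: below 77% none; 77% to below 94% minor; 94% or more major.

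Note 1's interpolation then works from 95 cc upward without further change. Confirm that any submitted plan with a PTV above 95 cc was scored for D2cm against these upper limits. The cost is two table cells and that check; nothing in the design or analysis changes.
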